12.3.2 Period 1, Days 7 and 14 (or Early Termination Visit)

Patients will report to the study site on Days 7 and 14 (±1 day) and have the assessments/procedures listed below completed. Study personnel will administer a dose of the patient's blinded medication at the clinic on Days 7 and 14, so assessments can be performed according to the specified times in relation to the time of dose administration. The medication administered by study personnel should be the same as what the patient has been taking for Period 1. If the patient is taking study medication 3 or 4 times a day, the visit needs to be arranged such that one of the doses is administered by the study site personnel, and assessments should occur after the same dose each visit.

- Assessment of AEs/SAEs;
- Vital signs (seated position), including SBP, DBP, heart rate, respiration, and body temperature;
- Urine pregnancy test in females of childbearing potential (only on Day 14);
- Concomitant medications;
- Collect patient Drug Dosing Diary and perform IP accountability (a new Drug Dosing Diary is given to the patient on Days 7 and 14);
- Efficacy assessments following in-clinic dose of double-blind medication as listed below:

Order of Assessment at Each Study Visit (when applicable)	Start Time After Dose (+ 10 minutes unless otherwise specified)
HFSME	45 minutes
6-minute walk test	After HFSME
Time to rise from floor	After 6-minute walk
Time to rise from chair	After rise from floor
Time to climb 4 stairs	After rise from chair
Time to walk 10 meters	After climb stairs
Quality of Life Assessment	After 10-meters walk

• INQoL for neuromuscular disease or the PEDSQLTM assessments will be completed for adult or pediatric patients, respectively after the six other assessments have been made.

On Day 14, all Period 1 study medication should be collected after the assessments have been performed, and study medication for Period 2 dispensed. The first dose of Period 2 medication is to be administered after the assessments are completed and at the time of the next regularly scheduled dose.

12.4 Period 2, Days 21 and 28 (or Early Termination Visit)

Patients will report to the study site on Days 21 and 28 (± 1 day) and have the assessments/procedures listed below completed. Study personnel will administer a dose of the patient's blinded medication at the clinic on Days 21 and 28, so assessments can be

performed according to the specified times in relation to the time of dose administration. The medication administered by study personnel should be the same as what the patient has been taking for Period 2. If the patient is taking study medication 3 or 4 times a day, the visit needs to be arranged such that one of the doses is administered by the study site personnel.

- Assessment of AEs/SAEs;
- Complete physical exam (Day 28 only);
- Vital signs (seated position), including SBP, DBP, heart rate, respiration, and body temperature;
- 12-lead ECG (Day 28 only);
- Clinical laboratory tests (Day 28 only);
- Urine pregnancy test in females of childbearing potential (Day 28 only);
- Concomitant medications;
- Collect patient Drug Dosing Diary and perform IP accountability (a new Drug Dosing Diary is given to the patient on Day 21);
- Efficacy assessments following in-clinic dose of double-blind medication as listed below:

Order of Assessment at Each Study Visit (when applicable)	Start Time After Dose (+ 10 minutes unless otherwise specified)
HFSME	45 minutes
6-minute walk test	After HFSME
Time to rise from floor	After 6-minute walk
Time to rise from chair	After rise from floor
Time to climb 4 stairs	After rise from chair
Time to walk 10 meters	After climb stairs
Quality of Life Assessment	After 10-meters walk

• INQoL for neuromuscular disease or the PEDSQLTM assessments will be completed for adult or pediatric patients, respectively after the six other assessments have been made.

Page 53

On Day 28, all Period 2 study medication should be collected after the assessments have been performed. This represents the end of the study.

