9.6.6 Physical Examination

A complete physical examination is to be performed at each clinic visit or, if applicable, at early discontinuation from the study. Complete physical examination will include assessments of general appearance as well as the following:

- Head
- Eyes
- Ears
- Nose
- Throat
- Cardiovascular
- Dermatologic
- Lymphatic
- Respiratory
- Gastrointestinal
- Musculoskeletal

Weight will be measured with each physical examination throughout the study. Height (cm.) will be measured at screening only.

Other body systems may be examined. Clinically significant changes from baseline will be recorded as AEs

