10.3 Safety Blood Collection

Patients who experience a serious or severe AE should have, at the discretion of the Investigator, a blood sample drawn for safety labs as soon as possible after the AE began.

Additional blood sampling may be performed at any time during the study if warranted to monitor patient safety.

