12.2 Open-label Run-in

Amifampridine dose will be titrated upward every 3 to 4 days, starting at 15 mg/day, at the discretion of the Investigator. Patients will either visit or have telephone/video contact with the site for each dose titration and at least one in-person site assessment at Week 3 of the Run-in period (Table 1). When the Investigator determines that the patient has reached the maximal tolerable dose, the patient should demonstrate they can remain on a stable dose and frequency for at least an additional 7 days. The Open-label Run-in period may be extended if additional time is needed for dose titration. At the end of this period, patients must show a ≥3-point improvement in HFMSE from start of Run-in, to be eligible for randomization (Day 0).

Patients should be given a Drug Dosing Diary to record each dose of their open-label medication and instructions on how to complete the form.

Additional visits are allowed as necessary. Screening visit and start of Run-in (Day 1) may be combined into a single visit.

12.3 Period 1

12.3.1 Day 0

Patients who are deemed eligible for continuation will have the assessments/procedures listed below completed on Day 0 after taking a supervised dose of their medication for that day during the clinic visit, so that the assessments can occur in the prescribed relation to the time of medication administration.

- Confirmation of Inclusion/Exclusion criteria;
- Assessment of AEs/SAEs;
- Complete physical exam with weight;
- Vital signs (seated position), including SBP, DBP, heart rate, respiration, and body temperature;
- Standard resting 12-lead ECG;
- Clinical laboratory tests including hematology, chemistry, and urinalysis;
- Urine pregnancy test in females of childbearing potential only;
- Concomitant medications;
- Collect patient Drug Dosing Diary and perform IP accountability of open-label medication;
- Efficacy assessments following in-clinic dose of open-label medication as listed below:

Order of Assessment at Each Study Visit (when applicable)	Start Time After Dose (+ 10 minutes unless otherwise specified)
HFSME	45 minutes
6-minute walk test	After HFSME
Time to rise from floor	After 6-minute walk
Time to rise from chair	After rise from floor
Time to climb 4 stairs	After rise from chair
Time to walk 10 meters	After climb stairs
Quality of Life Assessment	After 10-meters walk

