14.2 Analysis Populations

The following analysis populations will be defined for the study:

- Safety Population: The safety population will consist of all subjects who are enrolled in the study and have received at least one dose of amifampridine and includes subjects who begin the Run-in period regardless of whether they are randomized to double blind medication on Day 0.
- Full Analysis Set (FAS): This population consists of all randomized subjects who
 receive at least 1 dose of IP (amifampridine or placebo) and have at least one posttreatment efficacy assessment. Subjects will be compared for efficacy according to
 the treatment to which they were randomized, regardless of the treatment actually
 received.
- Per Protocol (PP): This population is a subset of the FAS population, excluding subjects with major protocol deviations. The PP population will include all FAS subjects who:

- Have no major protocol deviations or inclusion/exclusion criteria deviations that might potentially affect efficacy, and
- o Subjects who took at least 80% of the required treatment doses.
- The PP population will be determined before database lock and unblinding subject treatment codes.

The FAS population will be the primary analysis set for all effectiveness analyses. The safety population will be used for the analysis of all safety variables and baseline characteristics. The PP population will be used for selected effectiveness analyses.

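### No ECG or routine laboratory test is required when a patient stops early, and Section 9.6.6 contradicts the visit lists on the physical exam

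*Protocol*

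**What the plan says.** Two protocol procedure lists also serve patients who stop early. The heading of one reads "12.3.2 Period 1, Days 7 and 14 (or Early Termination Visit"), and the heading of 12.4 carries the same addition for Period 2.

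- **12.3.2 (Period 1):** AEs, vital signs, a pregnancy test on Day 14, concomitant medications, diary and drug accountability, and efficacy tests. ECG, laboratory tests and physical exam are not listed.
- **12.4 (Period 2):** all three are listed, but each is restricted to the last visit: "12-lead ECG (Day 28 only"), "Clinical laboratory tests (Day 28 only"), and the physical exam likewise.
- **Table 1 and SAP Appendix 1:** ECG, laboratory tests and physical exam at Screening, Day 0 and Day 28, with no early-termination column. SAP 10.12.3 and 10.12.4 repeat these three visits for ECG and exam.
- **9.6.6:** "A complete physical examination is to be performed at each clinic visit or, if applicable, at early discontinuation from the study".
- **10.3:** "Patients who experience a serious or severe AE should have, at the discretion of the Investigator, a blood sample drawn for safety labs". The section also permits further blood sampling at any time if patient safety warrants it.
- **12.2 (run-in):** extra visits are allowed, but no exit visit is defined. The Week 3 visit in Table 1 has vital signs and AEs but no ECG or laboratory tests.
- **12.3.1 (Day 0):** "Patients who are deemed eligible for continuation will have the assessments/procedures listed below completed on Day 0".
- **14.2:** the Safety Population "includes subjects who begin the Run-in period regardless of whether they are randomized to double blind medication on Day 0".

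**The concern.** Safety and tolerability form a primary objective, and SAP 10.12 summarizes observed safety data without imputation. A test that is not scheduled when a patient stops is missing because the patient stopped, and Section 9.2.3 names a serious or intolerable AE as a reason for stopping. Section 7.4.3 counts QTc prolongation (2 of 1,454) and abnormal liver enzymes (6 of 1,454) among the clinically significant or serious events seen with the drug. Sections 9.6.3 and 9.6.5 make clinically significant laboratory and ECG findings reportable as AEs, which can happen only if the test is done. If sites follow the lists literally, the ECG and laboratory summaries lean towards patients who tolerated treatment. With about 12 randomized patients, one or two missing values are visible in any table.

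**Working it through.** There is no plan figure to reproduce. The check sets the sections side by side.

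**Step 1. What is required at early termination after randomization**

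| Item | 12.3.2 | 12.4 | Elsewhere |
|---|---|---|---|
| ECG | not listed | Day 28 only | nothing |
| Laboratory tests | not listed | Day 28 only | 10.3, discretionary |
| Physical exam | not listed | Day 28 only | 9.6.6 requires it |
| Vital signs | listed | listed | – |
| AEs/SAEs | listed | listed | – |

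ECG and laboratory tests are each required by 0 of the 2 lists and by no other section. The exam is required by 0 of the 2 lists but is required by 9.6.6. For the exam the fault is therefore a contradiction. Section 9.6.6 also asks for an exam at every clinic visit, which Table 1 does not schedule.

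**Step 2. Required ECG and laboratory sets per patient (Table 1)**

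- Completer: Screening + Day 0 + Day 28 = 3.
- Randomized, stops before Day 28: Screening + Day 0 = 2, so none after randomization.
- Misses the 3-point HFMSE gain on Day 0: Screening + Day 0 = 2, of which the Day 0 set is on open-label drug.
- Stops in run-in before Day 0: Screening = 1, taken before study drug, so 0 on-drug.

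**Step 3. Why HFMSE failures have the Day 0 set**

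Section 9.1.1 has the Table 1 Day 0 procedures done in order to confirm eligibility. Table 1 (footnote b) and Section 9.3.3 place safety assessments before the clinic dose and HFMSE 45 minutes after it, so the ECG and blood draw precede the result that decides failure. The lead-in to 12.3.1 limits the list to patients already judged eligible and places all of it after the dose. That same list contains the eligibility check and the HFMSE itself, so it cannot sensibly mean only patients who have passed. The wording needs reconciling, but the data are provided for.

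**Step 4. What Day 28 gives completers**

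In the amifampridine-then-placebo sequence, Day 28 follows 28 − 14 = 14 days of placebo, and no ECG or laboratory test is scheduled on Day 14. The last on-drug set of those completers is Day 0. Only the placebo-then-amifampridine sequence has Day 28 values on drug.

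**Step 5. What the SAP would do with early-termination values**

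SAP 10.7 uses nominal-visit data for by-visit summaries and promises early-discontinuation data only in listings. SAP 10.12.5 summarizes laboratory values by sequence and visit, and Period 1 has no laboratory visit after Day 0. SAP 11.2 would use assessments made at discontinuation for that period, but does not require them. Run-in exits have no sequence. Adding a column to the schedule would not, by itself, bring the new values into the tables.

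**The case against.** The best reply is that the protocol leaves room for sensible practice. Section 10.3 permits extra blood sampling at any time, 12.2 allows extra run-in visits, 9.6.3 has clinically significant laboratory results repeated at the investigator's discretion, and 10.1 follows unresolved AEs to resolution or stability. Section 9.6.6 already requires the exam. Every randomized patient has an on-drug ECG and laboratory set on Day 0, after at least 7 days at a stable dose. All of this stands, and it limits the damage. It does not supply a requirement. The blood sampling is discretionary, its explicit trigger is a serious or severe AE (an intolerable but non-severe one does not meet it), and nothing prompts an ECG.

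Two stronger readings are tempting and are not supported. A reader might infer that every run-in failure leaves without a safety assessment and count all of them as lacking on-drug data. Step 3 shows that those who fail on Day 0 have the set, so only exits before Day 0 are affected. A reader might also infer that completers get end-of-exposure data which early terminators are denied. Step 4 shows that this is untrue for one of the two sequences. The Day 28 set is an end-of-study set.

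**Conclusion.** The point holds in a limited form. ECG and routine laboratory tests are not required at early termination in either double-blind period, or at run-in exit before Day 0. The physical exam requirement in 9.6.6 conflicts with Table 1, 12.3.2, 12.4 and SAP 10.12.4. Per patient, a randomized early terminator loses one of three planned sets and has none after randomization. A pre-Day 0 exit may have no on-drug ECG or laboratory value at all. The total effect cannot be sized, because the documents give neither a discontinuation rate nor a rate of run-in exit before Day 0. The conclusion assumes that sites follow the lists as written; an investigator using discretion would narrow the gap. This should be corrected because safety is a primary objective and the remedy is small. It does not undermine the design.

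**What to change.** 1. Add an Early Termination column to Table 1 and SAP Appendix 1 carrying the Day 28 safety set: physical exam, vital signs, ECG with QTc, laboratory tests, pregnancy test where applicable, AEs and concomitant medications.
2. In 12.4, change the Day 28 restriction on ECG, laboratory tests, exam and pregnancy test to Day 28 or Early Termination. In 12.3.2, add the same items for early termination.
3. In 12.2, state that a patient who stops open-label drug before Day 0 has this set at the last visit.
4. Reword 12.3.1 so that the Day 0 set applies to every patient who reaches Day 0, in line with 9.1.1 and Table 1. Reconcile 9.6.6 with Table 1, and SAP 10.12.3 and 10.12.4 with the revised schedule.
5. In SAP 10.7, state that early-termination ECG and laboratory values are summarized by the treatment being taken at the time, with run-in exits shown as not randomized, and are not confined to listings.

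The cost is a wording amendment. A randomized early terminator has a set already planned for Day 28 that would otherwise be forgone. A run-in exit adds one routine ECG and blood draw, and possibly a visit, since none is now defined. No dose or treatment rule changes.

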13 DATA QUALITY ASSURANCE

Catalyst personnel or designees will visit the study site before initiation of the study to review with the site personnel information about the IP, protocol and other regulatory document requirements, any applicable randomization procedures, source document requirements, CRFs, monitoring requirements, and procedures for reporting AEs/SAEs.

At visits during and after the study, a CRA will monitor the site for compliance with regulatory documentation, with a focus on accurate and complete recording of data on CRFs from source documents, adherence to protocol, randomization AE/SAE reporting, and drug accountability records.

14 STATISTICAL METHODS AND DETERMINATION OF SAMPLE SIZE

14.1 Statistical and Analytical Plans

14.1.1 Interim Analyses

No interim analyses are planned.

14.2 Analysis Populations

The following analysis populations will be defined for the study:

- Safety Population: The safety population will consist of all subjects who are enrolled in the study and have received at least one dose of amifampridine and includes subjects who begin the Run-in period regardless of whether they are randomized to double blind medication on Day 0.
- Full Analysis Set (FAS): This population consists of all randomized subjects who
 receive at least 1 dose of IP (amifampridine or placebo) and have at least one posttreatment efficacy assessment. Subjects will be compared for efficacy according to
 the treatment to which they were randomized, regardless of the treatment actually
 received.
- Per Protocol (PP): This population is a subset of the FAS population, excluding subjects with major protocol deviations. The PP population will include all FAS subjects who:

- Have no major protocol deviations or inclusion/exclusion criteria deviations that might potentially affect efficacy, and
- o Subjects who took at least 80% of the required treatment doses.
- The PP population will be determined before database lock and unblinding subject treatment codes.

The FAS population will be the primary analysis set for all effectiveness analyses. The safety population will be used for the analysis of all safety variables and baseline characteristics. The PP population will be used for selected effectiveness analyses.

14.3 Primary Endpoint

The primary efficacy endpoint of the study is the change in HFMSE score from Day 0 (baseline) for SMA subjects treated with amifampridine and placebo.

14.4 Secondary Endpoints

The secondary efficacy endpoints of the study are:

- the six-minute walk test
- timed tests
- quality of life assessments

14.5 Safety Analysis

Prior to analysis, all AEs will be coded using the MedDRA coding dictionary. Based on these coded terms, TEAEs and SAEs will be summarized using system organ class and preferred terms, as well as by relationship to treatment. All AEs will be listed, regardless of whether they were study treatment related.

Vital signs will be summarized using descriptive statistics (mean, standard deviation, median, minimum, maximum, and number of non-missing observations) by time point. Changes from baseline will also be summarized by post-dose time point.

Clinical laboratory parameters will be summarized using descriptive statistics (mean, standard deviation, median, minimum, maximum, and number of non-missing observations) by time point. Changes from baseline will also be summarized by post-dose time point. In addition, a shift table will be constructed to show the shifts in laboratory results by parameter relative to the normal ranges. The number and percentage of subjects with the following shifts will be presented: normal/normal, normal/low, normal/high, low/low, low/normal,

Page 55

low/high, high/low, high/normal, and high/high. Similar shift tables will also be constructed for physical exam results. ECG results will be summarized in a shift table with the following shifts presented: normal/normal, normal/abnormal, abnormal/normal and abnormal/abnormal. A table of descriptive statistics for QTc interval by treatment, day and period will be created.

Additional safety analyses may be performed as described in the SAP for the study.

14.6 Efficacy Analysis

14.6.1 Primary Efficacy Endpoint Analyses

The change-from-baseline scores [Change From Baseline (CFB)₇ = HFMSE₇ – HFMSE₀, CFB₁₄ = HFMSE₁₄ – HFMSE₀, CFB₂₁ = HFMSE₂₁ – HFMSE₀, CFB₂₈ = HFMSE₂₈ – HFMSE₀] will be analyzed using a mixed effects linear model. Treatment (amifampridine (A) or placebo (P)) and Sequence (A/P or P/A) and the Treatment by Sequence interaction will enter the model as fixed effects. Subject within Sequence will enter the model as a random effect with a block diagonal covariance structure. Population marginal means will be estimated for each of the four Period and Sequence combinations.

Other analyses may be carried out as specified in the Statistical Analysis Plan.

14.6.2 Secondary Efficacy Endpoint Analyses

The quantitative secondary efficacy endpoints (6-minute walk test, Time-to-rise-from-floor, Time-to-rise-from chair, Time-to-climb-4-stairs, and Time-to-walk-10 meters) will be analyzed as the HFSME is analyzed. The four CFB scores will be analyzed with a linear mixed model. Treatment and Sequence will be entered as fixed effects. Subject within Sequence will be entered as a random effect with a block-diagonal covariance structure. Population marginal means will be estimated for each of the four Period and Sequence combinations.

Results from INQoL questionnaires and PEDSQL TM inventory of disease specific symptoms will be summarized with descriptive statistics (n, mean, standard deviation, minimum, median, and maximum) per time point (Days 0, 7, 14, 21, and 28) and CFB, using the Day 0

¹ Also known as "LSMEANS".

Page 56

response as the baseline level). The subscales of the QoL questionnaires will be similarly summarized.

14.7 Determination of Sample Size

The sample size for this study is based on clinical considerations related to the epidemiology of the disease, and not on a formal statistical power calculation. The sample size should be representative of a sufficient number of patients to evaluate the study objectives (i.e. safety, tolerability, and evidence of efficacy of amifampridine in the target population). It is anticipated approximately 12 patients will be randomized.

14.8 Changes in the Conduct of the Study or Planned Analyses

Any change in study conduct considered necessary by the Investigator will be made only after consultation with Catalyst., who will then issue a formal protocol amendment to implement the change. The only exception is when an Investigator considers that a patient's safety is compromised without immediate action.

Protocol amendments that influence patient risk or the study objectives, or require revision of the ICF, must receive approval from the IEC prior to their implementation.

When a protocol amendment substantially alters the study design or the potential risks or burden to patients, the ICF will be amended and approved by Catalyst and the IEC, and all active patients must again provide informed consent.

Note: If discrepancies exist between the text of the statistical analysis as planned in the protocol, and the final SAP, a protocol amendment will not be issued, and the SAP will prevail.

